8.3. Definition of Adverse events

An adverse event is defined as any untoward medical occurrence in a subject participating in a clinical study, whether or not there is a causal relationship with the IMP and/or experimental procedures, occurring or detected from the date the participant signs the information and consent form, irrespective of the period of the study (periods without administration of the IMP (e.g. run-in period) are also concerned).

An adverse event can therefore be:

- any unfavourable and unintended sign (including an abnormal finding from an additional examination such as lab tests, X-rays, ECG, ...) which is deemed clinically relevant by the investigator,
- any symptom or disease,
- any worsening during the study of a symptom or a disease already present when the participant entered the study (increase in frequency and/or intensity), including the studied pathology,

and detected during a study visit or at an additional examination or occurred since the previous study visit (including relevant event reported in participant's diary or safety evaluation scale).

Of note:

Any hospitalisation for administration of anti-tumoral treatment and/or associated protocol (during or after the study) or other care measures for cancer (e.g. overnight hospital stay to receive a blood or platelets transfusion), for social reasons, educational purpose (e.g. learning of diabetes management by the participant) or routine check-up should not be considered as an adverse event and should not be reported in the e-CRF. The following procedures, whether planned before the study or not, whether leading to a hospitalisation or not, **should not be reported in the e-CRF and kept in the source data (or patient file):**

- therapeutic procedures related to a non-aggravated medical history (e.g. cataract extraction not due to an aggravation of the cataract during the study, haemodialysis sessions related to a renal insufficiency not aggravated during the study),
- prophylactic procedures (e.g. sterilisation, wisdom teeth removal),
- comfort procedures (e.g. cosmetic surgery),
- control procedures of a pre-existing condition without aggravation (e.g. colonoscopy to control the remission of colon cancer).

8.4. Definition of Serious adverse events

Any adverse event that at, any dose:

- results in death,
- is life-threatening⁽¹⁾,
- requires inpatient hospitalization or prolongation of existing hospitalization,
- is medically significant⁽²⁾,
- results in persistent or significant disability/incapacity⁽³⁾,
- is a congenital anomaly/birth defect⁽⁴⁾.

⁽¹⁾ Life-threatening in this context refers to an event in which the participant was at risk of death at the time of the event; it does not refer to an event which hypothetically might have caused death if it were more severe.

⁽²⁾ Any event that might not be immediately life-threatening or result in death or hospitalisation, but might jeopardise the participant or might require intervention to prevent one of these outcomes (for example: oedema or allergic bronchospasm that required intensive treatment at home, blood dyscrasias, convulsions that do not result in hospitalisation, or development of drug dependence or drug abuse). The investigator should exercise his/her scientific and medical judgement to decide whether or not such an event requires expedited reporting to sponsor.

⁽³⁾ Disability/incapacity in this context refers to any event that seriously disrupts the ability of the participant to lead a normal life, in other words leads to a persistent or permanent significant change, deterioration, injury or perturbation of the participant's body functions or structure, physical activity and/or quality of life.

⁽⁴⁾ Congenital anomaly or birth defect refers to the exposure to the IMP before conception (in men or women) or during pregnancy that resulted in an adverse outcome in the child.

8.5. Definition of Overdose

This refers to any intake of a quantity of IMP or a product other than the IMP taken as part of the protocol (NIMP) which is above the maximum dose recommended in the study protocol, independently of the occurrence of any adverse event.

The quantity should be considered per administration or cumulatively regarding the maximum dose recommended in the study protocol or in ALL-MB 2015 protocol for NIMP.

8.6. Definition of Adverse event of special interest

Not applicable

8.7. Definition of Events requiring an immediate notification (ERIN)

An event must be **notified immediately** (i.e. without delay and within 24 hours at the latest) to the sponsor if it is:

- a serious adverse event,
- an overdose of the IMP/NIMP even if asymptomatic,
- any intake of the IMP/NIMP by a person around the participant,
- a pregnancy.

8.8. Classification of an adverse event (seriousness, severity, causality, expectedness)

It is important that the investigator gives his/her own opinion regarding the **seriousness**, the **severity** of the event as well as the **cause-effect relationship** between an adverse event and the research (IMP or study protocol). This evaluation must be assessed by the investigator and reported in the AE form. In addition, the sponsor will be responsible for the evaluation the **expectedness** of the event (See [Section 8.9.3](#)).

The Seriousness should be evaluated according to international guidances (see definition [Section 8.4](#), in accordance with [ICH Topic E2A](#) and [DIRECTIVE 2001/20/EC OF THE EUROPEAN PARLIAMENT AND OF THE COUNCIL of 4 April](#)).

The severity of all AEs will be graded according to the National Cancer Institute Common Toxicity Criteria for Adverse Event (NCI-CTCAE) on a five-point scale (Grade 1 to 5):

- Grade 1: Mild; asymptomatic or mild symptoms; clinical or diagnostic observations only; intervention not indicated.
- Grade 2: Moderate; minimal, local or non-invasive intervention indicated; limiting age-appropriate instrumental ADL¹.
- Grade 3: Severe or medically significant but not immediately life-threatening; hospitalization or prolongation of hospitalization indicated; disabling; limiting self-care ADL².
- Grade 4: Life-threatening consequences; urgent intervention indicated.
- Grade 5: Death related to AE.

The cause-effect relationship

The investigator has to assess in the AE form if the AE is related or not to the research, meaning:

- adverse event related to IMP
- adverse event related to study protocol i.e. related to:
 - o a procedure scheduled in the study protocol (i.e. exercise test, MRI, etc.), or
 - o a change or withdrawal of previous / concomitant treatment related to the conditions of the protocol or
 - o a product other than the IMP, taken as part of the protocol (NIMP or other);

Moreover, the investigator has to assess if the AE is related to disease progression. Cases ticked “related” by the investigator or judged by the sponsor as having a reasonable suspected causal relationship to the IMP (AE linked to the mechanism of action of the IMP...), will be considered as suspected Adverse Drug Reaction. In general, if a relationship between AE and IMP is at least reasonably possible (i.e. the relationship cannot be ruled out) it is to be considered as “related”.

8.9. Reporting procedures

8.9.1. Time frame for AE reporting

Any event meeting the above mentioned definitions (see sections 8.3 to 8.7) must be reported to the sponsor on an adverse event form if it occurred:

- before the first intake of the IMP for events related to the research
- at any time after the administration of IMP, up to the participant's withdrawal visit for all events,
- up to 30 calendar days after the participant's last intake of IMP for all ERIN, regardless of the supposed role of the research.
- irrespective of the time of onset after the end of the study in case of serious adverse event related to the research.

[figure not shown]
Of note, events occurring between the signature of the informed consent and the first administration of the test drug for which the investigator does not consider an association with

¹ Instrumental Activities of Daily Living (ADL) refer to preparing meals, shopping for groceries or clothes, using the telephone, managing money, etc.

² Self-care ADL refer to bathing, dressing and undressing, feeding self, using the toilet, taking medications, and not bedridden”.

any procedure/condition required by the study protocol must be reported as **medical history** or as signs and symptoms related to the studied disease in the dedicated form of the CRF.

For a given patient, medical histories and adverse events already reported in the initial CL2-95014-002 study will not be reported in the eCRF, except in case of worsening.

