Objective(s): The primary objective of this study is to provide treatment with lyophilized S95014 in pediatric patients with ALL who completed the CL2-95014-002 study during the induction phase. Secondary objective is to assess the safety profile of lyophilized S95014 during the consolidation phase.	
Methodology: This is a multicentre, non-randomized roll-over study of lyophilized Pegaspargase (Oncaspar®, S95014) formulation in the treatment of pediatric patients with ALL. This study is designed to provide continued access to S95014 during the consolidation phase in patients who completed the CL2-95014-002 study and who are clinically benefitting from S95014 without major toxicity.	
Written informed consent and assent (when appropriate) will be obtained from each patient and/or his/her parent(s)/legal representative during the inclusion visit, corresponding to the withdrawal visit of the initial CL2-95014-002 study. Safety assessment including laboratory tests, ECG, cardiac imaging and pregnancy test performed during the withdrawal visit of the initial CL2-95014-002 study can be used to assess the inclusion in this roll-over study.	
The study duration will be approximately 7 months, including the treatment period consisting of the consolidation phase (approximately 6 months) and the follow-up period (30 days after the last S95014 infusion). After completing the consolidation phase, patient will be discontinued from the study and will be treated as per investigator's judgment.	
Lyophilized S95014 will be administered IV, over 1 to 2 hours, every two weeks during the consolidation phase at the dose of 1000, 2000 or 2500 U/m ² , as per investigator's judgment. Patients will be administered 9 infusions of lyophilized S95014, at week 7, 9, 11, 15, 17, 19, 23, 25 and 27 (3 phases S1, S2 and S3). Patients will receive other backbone chemotherapy agents as per ALL-MB 2015 protocol.	
Secondary objective of this roll-over study is to assess the safety profile of lyophilized S95014 during the consolidation phase. All adverse events regardless of grade or causality and severity will be collected after the	

Name of the sponsor: I.R.I.S.
Name of Finished Product: Lyophilized pegaspargase
Name of Active Ingredient: Pegaspargase S95014 Oncaspar®
informed consent is signed and during the entire treatment period.
Number of included participants: Planned: Approximately 88
Diagnosis and main criteria for inclusion:

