3. STUDY OBJECTIVES AND ENDPOINTS

The main objective of this roll-over study is to provide continued access to S95014 during the consolidation phase in patients who completed the CL2-95014-002 study and who are clinically benefitting from S95014 without major toxicity.

Secondary objective of this roll-over study is to assess the safety profile of lyophilized S95014 during the consolidation phase. All adverse events regardless of grade or causality and severity will be collected after the informed consent is signed and during the entire treatment period (see [section 8](#)).

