4. STUDY DESIGN

4.1. Investigational plan

4.1.1. Study plan

The present CL2-95014-003 study is a multicentre, non-randomized roll-over study of lyophilized Pegasparagase (Oncaspar®, S95014) formulation in the treatment of pediatric patients with ALL who completed the CL2-95014-002 study during the induction phase.

Written informed consent and assent (when appropriate) will be obtained from each patient and/or his/her parent(s)/legal representative during the inclusion visit, corresponding to the withdrawal visit of the initial CL2-95014-002 study.

[figure not shown]
Lyophilized S95014 will be administered every two weeks during the consolidation phase at the dose of 1000, 2000 or 2500 U/m², as per investigator's judgment. Patients will be administered 9 infusions of lyophilized S95014, at week 7, 9, 11, 15, 17, 19, 23, 25 and 27 (3 phases S1, S2 and S3). Patients will receive other backbone chemotherapy agents as per ALL-MB 2015 protocol.

The study duration will be approximately 7 months, including the treatment period consisting of the consolidation phase and the follow-up period. After completing the consolidation phase, patient will be discontinued from the study and will be treated as per investigator's judgment.

For more details about the statistical analyses please refer to the [section 10](#).

The study plan is shown in [Figure \(4.1.1\) 1](#).

Figure (4.1.1) 1 – Study plan

The study will be divided into the following periods for each participant:

- **Inclusion visit:** to obtain informed consent and check the inclusion/non-inclusion criteria. The inclusion visit of CL2-95014-003 study will correspond to the withdrawal visit of the initial CL2-95014-002 study.
- **Treatment period:** As per ALL-MB 2015 protocol, treatment period will start at Day 1 of the consolidation phase. Patients will be on treatment until the end of the consolidation phase, unless they meet a discontinuation criterion as described in [section 5.6.1](#).
- **Withdrawal visit:** up to 30 days after the last dose of S95014 during the consolidation phase. Patient will continue receiving backbone chemotherapeutic regimen as per ALL-MB 2015 protocol, according to physician's judgment.
- **Follow-up visit:** a contact or telephone call will be done approximately 30 days after the last S95014 infusion, except in case of consent withdrawal. Follow-up of adverse events and the patient's survival will be recorded.

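### New non-serious adverse events are collected only to a withdrawal visit that has no earliest day, so their observation after the last dose can vary from 0 to 30 days between patients

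*Protocol*

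**What the plan says.** **End of adverse event collection.** Protocol section 8.9.1 has adverse events reported "at any time after the administration of IMP, up to the participant's withdrawal visit for all events". After that visit, two groups are still collected. Events requiring immediate notification (serious events, overdose, pregnancy, intake by another person) are reported for 30 calendar days after the last dose. Serious events related to the research are reported whenever they occur. Section 8.1 uses the same visit as the end point for recording significant abnormalities.

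**Timing of the withdrawal visit.** Protocol 4.1.1 puts it "up to 30 days after the last dose of S95014 during the consolidation phase". SAP 1.2.1 also gives only the 30-day upper limit.

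**Follow-up contact.** Protocol 4.1.1 and 8.2 plan a contact or call about 30 days after the last infusion; SAP 1.2.1 puts it no earlier than day 30. The text speaks of following up adverse events. Table (4.1.2) 1 marks adverse events at both the withdrawal and the follow-up visit.

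**Laboratory samples.** In Table (4.1.2) 1 the samples taken on infusion days are all pre-dose. The next scheduled sample after the last infusion is at the withdrawal visit.

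**Objective and durations.** Section 3 states: "Secondary objective of this roll-over study is to assess the safety profile of lyophilized S95014 during the consolidation phase". It says that all adverse events "will be collected after the informed consent is signed and during the entire treatment period", with a reference to section 8. The synopsis states: "The study duration will be approximately 7 months, including the treatment period consisting of the consolidation phase (approximately 6 months"), plus a 30-day follow-up counted from the last infusion.

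**The concern.** Safety is the only outcome that this study analyses. An adverse event proportion is interpretable only if each patient's period of observation is known and reasonably uniform. Here the end of observation for non-serious events is a visit date that may fall anywhere in a 30-day range. A patient seen soon after the last infusion has little chance of a recorded late non-serious event; a patient seen on day 30 has the full period.

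The same holds for laboratory findings. Protocol 2.2.2 names raised transaminases, raised bilirubin, hypertriglyceridemia and hyperglycemia among the common grade 3 or higher events. Such findings can be non-serious, and the shift tables to the worst value depend on when the single scheduled post-infusion sample is taken.

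Under protocol 5.6.1, stopping the study drug early means leaving the study. The open-ended window therefore also applies to patients who stop for toxicity, whose course after exposure is of most interest.

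**Working it through.** **Inputs.** Infusions at weeks 7, 9, 11, 15, 17, 19, 23, 25 and 27 (protocol 6.1.1), each taken as day 1 of its week. Withdrawal visit on day w after the last infusion, with w from 0 to 30 (protocol 4.1.1). Month of 30.4375 days and inclusive counting (SAP 3.4.1).

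**1. The plan's own durations.** The stated figures are about 6 months of treatment and about 7 months in total.
- First to last infusion: (27 − 7) × 7 + 1 = 141 days; 141 / 30.4375 = 4.6 months.
- First infusion to last infusion plus 30 days: 141 + 30 = 171 days; 171 / 30.4375 = 5.6 months, against 7.
- Counting from week 1 of induction gives (27 − 1) × 7 + 1 = 183 days = 6.0 months, and 183 + 30 = 213 days = 7.0 months. Only this start reproduces both figures, but it lies before this study: "treatment period will start at Day 1 of the consolidation phase".
- With an inclusion visit assumed in week 5 or 6, the total to last infusion plus 30 days is 6.1 or 5.8 months.
- If S3 lasts 8 weeks, as the spacing of S1, S2 and S3 suggests, consolidation is 24 × 7 = 168 days = 5.5 months. On that assumption, about 6 months is fair rounding.

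The 7 months cannot be obtained as 6 + 1. The 30 days run from the last infusion, so they overlap whatever part of consolidation follows it.

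**2. Observation of non-serious events, completers.** From the first infusion it lasts 141 + w days: 141 at w = 0, 155 at w = 14, 171 at w = 30. The part that may be missing is up to 30 of 171 days (17.5%), all of it after the last exposure.

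**3. Patients who stop early.** The 30-day range is the same, but on a shorter base. After the week-11 infusion, observation is (11 − 7) × 7 + 1 + w = 29 + w days, so 29 to 59. After the first infusion alone it is 1 + w days, so 1 to 31.

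**4. Does the follow-up contact close the gap?**
- Section 8.9.1: all events only to the withdrawal visit.
- Section 8.1: significant abnormalities only to the withdrawal visit.
- Sections 4.1.1 and 8.2: follow-up of adverse events at the contact, with no mention of new ones.
- Table (4.1.2) 1: adverse events marked at the contact, without qualification.

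The table can be read as requiring new events; the text cannot readily be read so. Sites could act differently.

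**5. Would the SAP count later events?** SAP 3.5.1 ends the treatment-emergent period at day 30 or the date of withdrawal, taking the earlier, and bases its analyses on treatment-emergent events unless stated otherwise. If that date means the withdrawal visit, a serious event on day 20 after a visit on day 10 is collected under the protocol but left out of the tables. New non-serious events would be left out too, even if the protocol were changed to collect them.

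**The case against.** Several arguments carry weight.

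- **The visit is probably meant to fall near the end of consolidation.** Protocol 6.2 has the investigator propose maintenance-phase treatment at the withdrawal visit, and 4.1.1 has the patient leave the study after consolidation. For completers an early visit may be uncommon. This makes the extremes of the range less likely, but no text requires it, and it does not help patients who stop early.
- **An upper limit alone suits patients who stop early**, who may need to be seen promptly. This stands, and is why a lower limit should apply only to completers.
- **The objective does not contradict section 8.9.1.** The sentence in section 3 refers the reader to section 8. This stands: the point is uneven observation, not a broken promise.
- **The loss is limited.** Serious events are covered to day 30, and section 8.2 foresees local laboratory tests between visits. This stands. The withdrawal sample is the only scheduled one, not the only possible one.
- **Some material is not available here.** The study-plan figure, a figure in 8.9.1 and the ALL-MB 2015 appendix are missing from the text reviewed and may bear on timing.

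Two stronger readings are tempting. A reader might infer that S3 will look safer than S1 and S2, since each of those is followed by four weeks of observation after its third infusion. No analysis by phase is planned; the adverse event tables are overall and by dose level. A reader might also infer that a definite number of consolidation days goes unobserved. That needs the end week of consolidation, which the available text does not give, or requires an approximate 6 months to be taken as exact. Neither reading is supported.

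**Conclusion.** The concern holds as a gap in uniform collection. Observation of new non-serious events after the last dose may be anything from 0 to 30 days, depending on the visit date. For completers this is up to 17.5% of the 171 days from first infusion to day 30 after the last; for early stoppers the share is larger. These are limits set by the wording, not a forecast of actual visit dates, and they do not depend on when consolidation ends. The schedule table and the text conflict on what the follow-up contact collects. The effect on the SAP tables assumes that its date of withdrawal means the withdrawal visit.

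This does not undermine the study. It is a descriptive continued-access study in which serious events remain covered, and the change is a worthwhile low-cost improvement. The 7-month duration is a minor restatement; the 6-month figure can be defended as rounding.

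**What to change.** 1. **Protocol 8.9.1, second time frame:** report all adverse events until 30 days after the last S95014 infusion. Align section 8.1.
2. **Protocol 4.1.1 and 8.2:** state that the follow-up contact collects new as well as ongoing adverse events, in agreement with Table (4.1.2) 1. Adopt the SAP's timing of no earlier than day 30, so that the contact covers the whole window.
3. **Protocol 4.1.1 and SAP 1.2.1:** give the withdrawal visit of completers a lower as well as an upper day limit, so that the last scheduled laboratory sample is taken at a comparable time.
4. **SAP 3.5.1:** end the treatment-emergent period at a fixed 30 days after the last infusion. Without this, the added events would not reach the tables.
5. **Synopsis and 4.1.1:** restate the study duration from the week schedule.

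The cost is a wording amendment to both documents and a few more non-serious events to enter. The visit and the contact are already planned, and no treatment changes. Patients who withdraw consent remain outside the contact, as now.

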5. INCLUSION AND WITHDRAWAL OF PARTICIPANTS

5.1. Inclusion criteria

1. Patient who completed the CL2-95014-002 study
2. Patient currently receiving clinical benefit from previous treatment with S95014 as per investigator's judgment
3. Informed consent obtained as described in [section 13.3](#) of the protocol
4. Women of childbearing potential (WOCBP) must use a highly effective method of birth control (both described in [section 5.3](#)) during study treatment and for 6 months after the last dose of IMP. In case of use of oral contraception women should have been stable on the same contraceptive drug (i.e. same active principle) for at least 1 month prior to the first IMP administration. In case of use of hormonal contraception, WOCBP and male participants with WOCBP partners should use a second method of contraception, also called barrier method, such as male or female condoms, cap, diaphragm or sponge with spermicide. However, since there is a potential for an indirect interaction between S95014 and oral contraceptives, the concomitant use of S95014 and oral contraceptives is not recommended. A method other than oral contraceptives should be used in WOCBP.
5. Male participants with WOCBP partners must use a condom during the study and until at least 6 months after the last dose of IMP. In addition, contraception should be considered for their female partners. Contraceptive measures do not apply if the participant is sterile, vasectomized or sexually abstinent. Sperm donation will not be allowed during the study and for 6 months after the last dose of IMP.

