8.9.2.2. Follow-up of adverse events

The investigator must ensure that follow-up of the participant is appropriate to the nature of the event, and that it continues until resolution if deemed necessary.

Any change in terms of diagnosis, intensity, seriousness, measures taken, causality or outcome regarding an adverse event already reported must be written up in a new complete evaluation of the event documented on an “Adverse event” page previously created for the event.

If the adverse event has not resolved at the participant's final visit in the study, the participant must be followed up suitably and any information on the outcome of the event will be noted on an « Adverse Event » page previously created for the event

If the follow-up of the participant is not done by the investigator him/herself (hospitalisation, followed by a specialist or the participant's general practitioner, ...), the investigator will do everything to establish/maintain contact with the person/department in charge of follow-up of the participant.

8.9.2.3. Special situations (pregnancy, overdoses, intake of IMP/NIMP a person around the participant)

Pregnancy

If a female participant in the study becomes pregnant, the investigator must:

- stop immediately the test drug (if the pregnancy is a non-inclusion criterion),
- report it on an « Adverse Event » page as well as on the specific paper pregnancy form (1st page) to be notified immediately (ERIN),
- contribute to the follow-up of this pregnancy and provide the sponsor with information concerning this follow-up (notably using the 2nd page of the specific paper pregnancy form).
- If the partner of a participant becomes pregnant during the course of the study, the pregnancy should not be reported in the e-CRF. The investigator should **immediately** contact the sponsor (contact details provided in the investigator's study file) who will inform him/her about the procedure to be followed.

Overdose of IMP or NIMP

- In case of overdose, the investigator should report it on an “Adverse Event” page to be notified immediately (ERIN).

- Overdose should be followed-up to ensure that the information is as complete as possible with regards to:
 - o dose details (number of units, duration...) and, if multiple overdose, details regarding other medicinal products or substance,
 - o context of occurrence, i.e. intentional (suicide attempt, other reason) or accidental (error in prescription, administration, dispensing, dosage),

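### Required pregnancy notification stops 30 days after the last dose although contraception is required for 6 months, so about 153 of 183 post-dose days carry no required pregnancy report

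*Protocol*

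**What the plan says.** **Pregnancy is an ERIN.** Protocol 8.7 states "An event must be notified immediately (i.e. without delay and within 24 hours at the latest) to the sponsor if it is" one of four listed items; pregnancy is the fourth.

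**The reporting window is 30 days.** Protocol 8.9.1 sets the limit for these events at "up to 30 calendar days after the participant's last intake of IMP for all ERIN, regardless of the supposed role of the research". It has one open-ended category: "irrespective of the time of onset after the end of the study in case of serious adverse event related to the research".

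**The contraception period is 6 months.** Protocol 5.1 requires highly effective contraception for women of childbearing potential "during study treatment and for 6 months after the last dose of IMP". Male participants with partners of childbearing potential "must use a condom during the study and until at least 6 months after the last dose of IMP". Sperm donation is barred for the same 6 months.

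**Pregnancy procedures are tied to the study.** Protocol 8.9.2.3 opens its participant clause with "If a female participant in the study becomes pregnant, the investigator must"; what follows includes an adverse event page, a pregnancy form and a contribution to follow-up. The partner clause begins "If the partner of a participant becomes pregnant during the course of the study" and sends the investigator to the sponsor, outside the e-CRF. Neither clause mentions the 6 months.

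**Birth defects are serious events.** The footnote in Protocol 8.4 reads "Congenital anomaly or birth defect refers to the exposure to the IMP before conception (in men or women) or during pregnancy".

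**The last planned contact** is a visit or telephone call about 30 days after the last infusion (Protocol 4.1.1 and 8.2; SAP 1.2.1).

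**The concern.** The protocol asks families to avoid conception for 6 months after the last dose, but asks investigators to report a pregnancy for only the first 30 days of that time. If an adolescent participant conceives in month 3, nothing in 8.9.1 requires the investigator to notify the sponsor, complete the pregnancy form or follow the pregnancy to outcome.

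What is at stake is outcome information on pregnancies conceived soon after exposure. Section 8.4 shows that the sponsor wants to know about birth defects after pre-conception exposure in either sex. A birth defect reported alone, without the uncomplicated pregnancies beside it, has no denominator. Safety is also the only objective in this study that is assessed (Protocol 3).

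**Working it through.** The plan gives no figure to reproduce. The check compares day counts, then asks what share of the period they represent.

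**Inputs**
- Pregnancy reporting after the last dose: 30 days (Protocol 8.7 with 8.9.1).
- Contraception after the last dose: 6 months (Protocol 5.1).
- Days per month: 30.4375 (the conversion in SAP 3.4.1).
- Treatment length T for a completer: week 7 to week 27, 20 × 7 = 140 days (Protocol 6.1.1); or nominally about 6 months, 182.6 days (Protocol synopsis).
- Conception rate: not given. A constant rate is assumed, so that shares of days stand in for shares of conceptions.

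**Post-dose period**
- 6 × 30.4375 = 182.6 days.
- Covered: 30 / 182.6 = 16.4%.
- Not covered: 182.6 − 30 = 152.6 days; 152.6 / 182.6 = 83.6%.

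**Treatment plus 6 months**

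Uncovered share = 152.6 / (T + 182.6).
- T = 140: 152.6 / 322.6 = 47.3%.
- T = 182.6: 152.6 / 365.25 = 41.8%.

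For a completer, less than half of the whole period is uncovered. Three further assumptions could change that:

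| Assumption | Result |
|---|---|
| Recognition, not conception, must fall by day 30 | Share = 1 − (T + 30 − lag) / (T + 182.6). It passes 50% at T = 140 once the lag exceeds 8.7 days. A 28-day lag gives 56.0% (T = 140) or 49.5% (T = 182.6) |
| Treatment stops early | 51.8% after 7 infusions (152.6 / 294.6, with T = 112); 49.5% after 8; 83.6% after 1 |
| Conception rate is higher after day 30 | The rate must exceed 170 / 152.6 = 1.11 times the earlier rate (T = 140) or 212.6 / 152.6 = 1.39 times (T = 182.6) |

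The documents do not settle any of these. Section 8.9.1 dates an event by when it occurred, without saying whether a pregnancy occurs at conception or at recognition.

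**Does another passage close the gap?**
- Related serious events (8.9.1) have no time limit, and 8.4 includes birth defects. A pregnancy is not in itself a serious event under 8.4, so an uncomplicated one does not qualify.
- Section 8.9.2 asks investigators to pass on new information that could matter to benefit-risk, with no stated end. One uncomplicated pregnancy would not clearly meet that test.
- Section 8.9.2.3 contains no 6-month extension, and no contact is planned after about day 30.

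None of these makes a pregnancy in months 2 to 6 notifiable as such.

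**The case against.** The strongest reply is that the two periods serve different purposes. Section 5.1 sets a precautionary contraception rule. It does not describe the 6 months as a period of established reproductive risk, and nothing in it says that reporting must match. The safety objective concerns the consolidation phase, and no planned analysis would change. This stands as far as it goes: the mismatch affects safety collection, not the validity of the descriptive analysis.

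A reader might infer more than the text supports, in three ways.
- *That most exposed conceptions escape safety collection.* The 84% applies only to post-dose days. Pregnancies during treatment and the next 30 days are reportable, which brings the uncovered share to about 42–47% for a completer at a constant rate. No conception rate or count of women of childbearing potential is given.
- *That nothing is reportable after day 30.* Related serious outcomes remain reportable without limit, and 8.8 counts an event as related unless a link can be excluded. The benefit-risk duty in 8.9.2 also continues. These routes depend on the investigator hearing of the event, but so would any passive extension.
- *That partner pregnancies are cut off at day 30.* Section 4.1.1 ends the trial at the last participant's last visit, so for earlier participants the partner clause could run well beyond their own day 30. It is ambiguous, not a proven cut-off.

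Two limits also stand. The age bands in SAP 3.3.3 do not show who is enrolled, since they run from newborns to 66 years and over; the contraception criteria and repeated pregnancy tests are better evidence that the question is relevant. In addition, the figure in 8.9.1, the consent pages, the pregnancy form and the investigator's study file were not available here, so whether families are already told to report later pregnancies cannot be judged.

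**Conclusion.** The mismatch is real in the text reviewed. Required pregnancy notification ends 30 days after the last intake, contraception runs for 6 months, and no passage bridges the two. About 153 of 183 post-dose days therefore have no required pregnancy report, form or outcome follow-up. The day count follows directly from the protocol, given the SAP's month length. The 42–47% share of treatment plus 6 months also needs a completer and a constant conception rate.

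What is lost is required notification of pregnancies without a related serious outcome. For partners, the period of required notification is unclear. The number of pregnancies involved is unknown and, in a paediatric study planned for approximately 88 participants, probably small. The point does not threaten the planned analyses. It is a gap in safety collection that can be closed cheaply and is worth closing.

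**What to change.** 1. In Protocol 8.9.1, separate pregnancy from the other ERIN. Make any pregnancy of a participant, or of a male participant's partner, reportable if conception occurs up to the end of the contraception period already set in 5.1, with follow-up to outcome.
2. In Protocol 8.9.2.3, replace the references to the study in the participant and partner clauses with that same period. This also removes the ambiguity about when the partner clause ends.
3. At the existing day-30 contact, remind families to report later pregnancies. Check that the participant and parent information says the same, and add a line if it does not.

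No visit, test or treatment rule changes. The SAP needs no change: its treatment-emergent window (SAP 3.5.1) ends no later than 30 days after the last infusion, so later reports would stay out of those tables. The cost is the wording, plus the handling of a few passive reports that may arrive after the last visit and go to pharmacovigilance. Because reporting would be passive, some late pregnancies would still be missed. If the sponsor prefers to keep 30 days, the protocol should explain why that differs from the contraception period.
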